PROTOCOL TITLE: Food Allergy Symptom Self-management with Technology (FASST) for Caregivers: An mHealth Intervention to Address Psychosocial Outcomes in Caregivers of Children with Food Allergy

NCT04512924

PRINCIPAL INVESTIGATOR: [name], PhD, MSN, RN (PI)

Document Date: 5/7/2021

Specific Aims

Overview: Caregivers of children with life threatening severe food allergic reactions are more likely to experience fatigue, depression and anxiety. These distressing psychosocial conditions, in turn, may impact child and family functioning. Unfortunately, there is a paucity of self-management tools for caregivers to address these consequences. This proposal leverages advances in mHealth to develop and test such a tool.

Approximately 6 million US children suffer from food allergy¹, an immune response that occurs reproducibly upon exposure to a given food. Food allergy is one of the fastest growing national public health concerns with incidence at 8% of children and prevalence increasing by 50% between 1997 and 2011.² Severe allergic reactions may include food-induced anaphylaxis (FIA), an acute life-threatening event affecting more than 40% of children diagnosed with food allergies.³ FIA can result in a rapid reaction that leads to circulatory collapse, coma, and death. Once a child experiences a food-induced reaction, of any severity, it is not possible to predict the severity of subsequent reactions but raises the risk of future fatal reactions.³ Between 2007 and 2016, FIA increased by 377% in the US, underscoring the need for better prevention and treatment² and for **interventions to address significant distress experienced by caregivers of children with food allergies.⁴**

Our recent preliminary research⁴ corroborates findings in the literature^{3; 5-11} suggesting that 32% of caregivers with a child who is newly diagnosed with food allergy(ies) experience clinically significant psychological distress.¹² Symptoms and related factors include fatigue, anxiety, depressed mood, social isolation, stress, and substantially reduced quality of life. Despite recognition that family caregivers of children with severe food allergies experience fatigue, adverse psychosocial conditions and decreased quality of life, there is a lack of caregiver-centered self-management interventions to address these outcomes. Moreover, a lack of self-management interventions for these caregivers means that these distressing symptoms will likely persist.

To address this gap, we propose to develop an intervention that specifically targets fatigue and associated psychosocial symptoms. Bounce Back Now (BBN)¹³, an existing technology-enhanced, self-management mHealth intervention designed to address disaster survivors' psychosocial health needs using a smartphone-formatted approach, will be tailored and adapted for caregivers of children with food allergy(ies), hence the renaming to **Food Allergy Symptom Self-Management with Technology (FASST)** for caregivers. Over the course of 6-months, we will conduct preliminary feasibility testing of FASST in a 4-week small randomized trial of 30 caregivers of children \leq 18 years-of-age who are newly diagnosed (\leq 90 days from diagnosis) with food allergy(ies).

Aim 1a: Perform key informant interviews (n = 10) and analyze via conventional content analysis to determine ways to improve app acceptability.

Aim 1b: Adapt FASST using data collected during key informant interviews.

Aim 2: Conduct preliminary testing of implementation processes including feasibility, acceptability, adherence and satisfaction using the RE-AIM framework with process measures, surveys, and key informant interviews in 30 caregivers randomized to receive FASST (n = 20) or the control condition (i.e., basic app with resource links) (n = 10).

Aim 3: Obtain estimates of variability and measure caregiver experienced fatigue, anxiety, depression, sleep, self-efficacy, and quality of life at baseline, 4-week intervention completion and 3-months post intervention.

B. Significance

B1. Food allergy is a highly complex condition and is growing in frequency and severity among children, negatively affecting quality of life.

Approximately 6 million children in the U.S. suffer from food allergy¹, and incidence is increasing.² Food-induced anaphylaxis (FIA) is a health risk associated with food allergy affecting more than 40% of children diagnosed with food allergies.³ FIA can result as a rapid reaction that leads to circulatory collapse, coma, and death. Once a child experiences a food-induced reaction, of any severity, it is not possible to predict the severity of subsequent reactions but raises the possibility of future fatal reactions.³ Although FIA reactions in children are rare, they are responsible for over 200 deaths and 30,000 emergency room visits annually in the United States.¹⁴ There is no cure for food allergies and treatment involves avoidance of food allergens and emergency treatment of symptoms caused by accidental exposure.¹⁵ A caregiver's ability to adhere to this standard of care may be challenged by a whole host of new factors that accompany the diagnosis, the most salient being the potential for a fatal reaction from ingestion of ubiquitous substances which are often invisible.

This creates an ever-present element of hypervigilance and stress-related fatigue as caregivers learn to manage food allergies as a chronic condition and as they learn to respond to food-induced reactions as an acute illness or event. Caregivers with newly diagnosed children are particularly challenged to balance appropriate vigilance and management strategies while tempering the effects of food allergy on quality of life.¹⁶

B2. Caregivers experience symptoms that may reduce caregiving effectiveness.

The PI's research, and that of others, highlights that caregivers of children with food allergy describe the physical challenges of care as overwhelming and constant. The perpetual hypervigilance and ensuing exhaustion associated with time-consuming and persistent condition-management activities – such as monitoring a child's food consumption at school or when with friends, shopping for, and preparing special food – have the greatest impact on caregiver quality of life and are associated with fatigue, uncertainty, constant stress, social isolation, reduced spontaneity, and persistent anxiety, fear, and depression.⁴⁻¹¹ Following diagnosis, caregivers experience a period of psychosocial adjustment where these symptoms are most pronounced.¹⁷ As caregivers begin to understand the necessary precautions and potential consequences of accidental ingestion associated with FIA and the required condition-management activities, fear and anxiety emerge as the predominant emotions. While a certain level of anxiety is essential for adequate management, high levels of sustained anxiety in caregivers of children with food allergy may be maladaptive, increasing the overall burden of caring for a child with FIA and negatively impacting the caregiver's ability to provide care to self, child, and family.¹⁸

B3. Self-management strategies for caregiver stress and fatigue are lacking.

Despite recognition that family caregivers of children with severe food allergies are at risk for adverse consequences, decreased quality of life, and diminished caregiving effectiveness, there are a lack of caregiver-centered self-management interventions to address stress-related fatigue, depression and anxiety symptoms. However, symptom self-management is exceedingly relevant to the caregiver of a child with newly diagnosed food allergy(ies) as management is complex and compounded by factors outside of the caregiver's control which are further intensified by the lack of definitive treatment or cure. The short-term goal of this technology-enhanced, self-management mHealth intervention is to enhance and promote effective self-management behaviors to improve the psychosocial well-being of the caregiver that in the long-term will lead to improved outcomes for the child, namely prevention of potentially fatal food induced reactions.

C. Innovation

This proposal is innovative because it is the first to address psychosocial manifestations of caregiving to children with newly diagnosed food allergy(ies) using a technology-based self-management scalable strategy that has the potential to be translated to other populations of caregivers of children with complex medical conditions. This proposal:

- Targets caregivers who are new to the disease process and management requirements and therefore have unique needs that will be addressed using a smartphone-formatted approach. This demonstrates an innovative approach that is both cost effective and sustainable over time (fewer personnel required).
- Focuses the intervention on psychosocial symptoms such as fatigue, addressing an unmet need recognized within the literature but neglected by providers.
- Uses a scalable strategy to engage caregivers during a critical time-period in the caregiving/condition trajectory (≤ 90 days from diagnosis) when psychosocial functioning is most at risk.
- Addresses barriers to accessing care such as transportation, work schedules, and childcare through the application of technology. Addressing these barriers lends to the translatability of the intervention to other populations of caregivers of children with complex medical conditions.
- Uses a technology-based intervention that has been tailored based on caregiver-reported needs and desires and provider expertise which is expected to increase engagement and reach of self-management strategy.

D. Approach

D1. Overview

This feasibility study is designed to modify an existing technology-enhanced, self-management mHealth intervention (BBN) and evaluate its impact on reach, self-management behaviors, caregiver psychosocial symptoms and quality of life targeting caregivers of children with newly diagnosed food allergy during the first 90 days after diagnosis. Our clinical sample will be recruited from the Medical University of South Carolina

(MUSC) Health Allergy and Immunology Clinic within the MUSC West Ashley Primary Care office. A sample of (n=10) caregivers of children with established food allergy (≥ 1 year from diagnosis) will be recruited for key informant interviews that will inform tailoring and adapting FASST. Feasibility (rate of recruitment, attrition, rate of missing data, adoption, implementation, satisfaction, acceptability) will be tested in a randomized sample (n=30) of caregivers of children newly diagnosed with food allergy (≤ 90 days from diagnosis). Participants (n=20) will be randomized to the experimental condition (FASST) or (n=10) to a control condition (i.e., basic app with resource links).

Participants randomized to the intervention arm (n=20) will receive the modified mHealth application (FASST) that contains elements of condition specific education and information, symptom self-monitoring, and symptom self-management. Participants in the control arm (n=10) will receive the modified mHealth application (FASST) that contains only the element of condition specific education and information.

D2. Investigative Team and Preliminary Work

D3.1. Setting, Sample and Recruitment. Prior to participant recruitment, we will tailor and adapt BBN to FASST based on existing literature and expertise of the study team. We will then recruit 10 caregivers of children with established food allergy (≥ 1 year from diagnosis) to participate in key informant interviews that will inform the most practical changes needed when tailoring and adapting FASST prior to the intervention. We consider these key informant interviewees as co-designers of FASST as they possess a level of experience with and understanding of food allergy management and the psychosocial consequences of caring for a child during the critical period following a child's food allergy diagnosis that caregivers of newly diagnosed children have yet to experience. Caregivers will be recruited via the Medical University of South Carolina (MUSC) Health Allergy and Immunology Clinic within the MUSC West Ashley Primary Care office. Caregivers will be recruited who have at least one child with an established food allergy(ies) diagnosis (≥ 1 year from diagnosis) and are familiar with the disease process and management as determined by: child has been seen at least every 12 months for one or more years. [name] will identify potentially eligible caregiver participants and will contact the caregiver, briefly describe the study, and ask permission for the principal investigator ([name]) or research assistant (RA) to contact the caregiver for screening. Once permission is granted, the PI or RA will contact the caregiver and assess for eligibility. Prior to consenting, all questions will be resolved to the patient's satisfaction. If a participant does not appear to understand the information contained within the consent document or of what is expected of them as a study subject, then a member of the study team will review the consent document again with the participant. If after this second review, the subject does not demonstrate an understanding, they will not be enrolled in the study. Only participants, with no observed cognitive impairment, will be consented and enrolled into the study.

Feasibility testing. Thirty caregivers of children with newly diagnosed (≤ 90 days from diagnosis) will be recruited into the feasibility Aim 2 of the study. Eligible caregivers will again be identified through the MUSC Health Allergy and Immunology Clinic. Inclusion criteria are as follows: caregivers of children ≤ 18 years-of-age who are newly diagnosed (≤ 90 days from diagnosis) with food allergy(ies). Only participants, with no observed

cognitive impairment, will be consented and enrolled into the study. To recruit participants for feasibility testing, [name] at the MUSC Health Allergy and Immunology Clinic will identify potentially eligible participants, explain study procedures, and if caregivers express interest, then will ask permission for the PI or RA to contact the potential participant. If permission is granted, the PI or RA will contact the potential participant to determine eligibility.

D3.2. Intervention

The intervention will be a multicomponent (3-part) technology-based package delivered via a mobile device and used over a 4-week period. The intervention will target influences and processes informed by the Caregiving Process Model. **Component 1** (education and support) will consist of continuous access to directed educational resources about food allergy and its management. These materials will be easily accessible via a mobile device and will include embedded PDFs and links to websites developed and tested by authoritative sources. An example includes education materials provided by the Food Allergy Education and Research (FARE), the leading national organization and most trusted source of food allergy information, programs and resources, such as the Food Allergy & Anaphylaxis Emergency Care Plan. To address potential literacy barriers, all resources will be provided in a web compatible format and compliant with current accessibility guidelines. **Component 2** (symptom monitoring and tracking) will consist of a mobile-device based application for daily tracking and monitoring of fatigue, anxiety and other psychosocial symptoms in caregivers of children with newly diagnosed food allergy(ies) that also permits upload of physical and emotional symptom logs to study personnel. The PI or RA will send a daily text reminder to participants randomized to the intervention arm of the study reminding them to complete their daily physical and emotional symptom log. Logged symptom trends will be graphically illustrated by the application for participant viewing. Based on feedback from component 2, participants will be given directed guidance related to component 3 (symptom self-management). **Component 3** will consist of symptom-based interventions participants can utilize real-time. For example, if a participant logs symptoms related to anxiety, the application will recommend a brief guided intervention for relaxation, such as meditation, or deep breathing. If a participant logs symptoms related to fatigue, the application will recommend the participant listen to a short audio clip that offers ideas for achieving better sleep or suggestions for good sleep hygiene. We will collect data via the app on the frequency and patterns of usage and will also collect measures data for Aim 3 at baseline, 4-weeks intervention completion and 3-months post-intervention completion. As well, the RA will send caregivers a weekly text message using a semi-structured protocol to “check in” with participants and promote engagement.

D3.3. Control group

The control group will receive Component 1 of the intervention.

D3.4. Primary Aim 1a and 1b: Key informant interviews and intervention tailoring and adaptation

We will use a purposive sampling strategy to identify caregivers of children with established (≥ 1 year from diagnosis) food allergy(ies) familiar with the disease process and management. Data obtained through key informant interviews using a semi-structured protocol and a qualitative descriptive approach²¹ will inform tailoring and adaptation of FASST. The purpose of interviews will be to obtain feedback from caregivers of children with established food allergy(ies) who have been managing the condition for one year or more. Participants will be asked about their experience in the first year of managing their child’s food allergy, with specific questions regarding the first 4 weeks of management and the perceived impact on their psychosocial well-being and overall quality of life. Participants will be shown a mocked-up application on a mobile device and asked to provide feedback related to the content. At the beginning of the session, the PI will deliver detailed verbal instructions regarding use of the device and intervention components. Participants will be provided with mobile devices that have been prepared for the feasibility testing (Aim 2) with access to the FASST application and text messaging. After allowing time for participants to explore the intervention (with direct observation), the PI will ask 8-10 open-ended questions with probes using an interview guide. Questions will be designed to assess the acceptability, feasibility, and usability of the intervention. The interview will conclude with questions regarding suggested improvements to the intervention. The hands-on, observational session is expected to last 45 to 60 minutes and the interview is expected to last an additional 45 to 60 minutes. The PI will video record observations to inform adaptation of the intervention. The interview will be audio recorded and transcribed. Following data analysis (described in **D3.7.**) the results from the interviews will be used to adapt the intervention to meet the specific needs of caregivers of children ≤ 18 years-of-age with a newly diagnosed food allergy(ies).

D3.5. Primary Aim 2: Feasibility Testing

To determine feasibility, we will apply the RE-AIM framework to assess the Reach, Efficacy, Adoption, Implementation, and Maintenance of the intervention with 30 caregivers.²² The domains are further explicated in Table 1. Participants will be asked to download the FASST app onto their mobile device with intervention components 1, 2, and 3 if randomized to the intervention arm and only component 1 if randomized to the control arm. The PI or RA will deliver detailed verbal instructions to the participants in both arms of the study on the use of the application and the respective intervention components. Participants will also receive written instructions and a contact number for technical assistance if needed. Baseline measures (Table 1) will be collected during the same meeting. Participants will participate in the intervention over a 4-week-period. At the end of the 4-week period, the PI will attend a post-intervention meeting with each individual caregiver participant during which measures data for Aim 3 will be collected. The PI will also collect frequency and patterns of usage data 3 months post-intervention to assess implementation and preliminary evidence of maintenance (Table 1). The PI will meet with the RA weekly during the intervention.

Post-intervention interviews. Five participants from each study arm will be randomly selected and asked to participate in post-intervention key informant interviews with the PI to obtain more in-depth data on accessibility, usability, and adherence to intervention guided by the RE-AIM framework (Table 1). Semi-structured interviews will be conducted in-person or via phone (participant's choice) using a qualitative descriptive approach,²¹ will last approximately 45-60 minutes, and will be conducted according to an interview guide with open-ended questions and probes.

Reimbursement for participants will be a \$50 gift card provided at each of the 3 data collection points, with participants in key informant interviews (pre- and post-intervention) receiving an additional \$50 gift card.

Measures. Caregivers will complete self-report measures at baseline, 4-week intervention completion, and 3 months post-intervention. Self-report measures will be collected during meetings between the PI and the participant. Participants will complete measures using a mobile tablet device. Data will be captured using REDCap data management system. The PI will be present to answer questions but will be unobtrusive while measures are completed.

Table 1: Intervention Domains and Measures

Major tasks and domains	Measures/instruments/questions and Cronbach's alpha ()	Data sources and time points
Demographics/clinical characteristics	Caregiver demographics including age, marital status, employment status, race/ethnicity, highest education level, and income; child age, health history, race/ethnicity, medications, health care utilization, rural/urban residence, insurance, family characteristics	Caregiver interview; baseline
Reach: Sample Recruitment	Monitoring of sample representativeness; types of recruitment activities; rates of recruitment; % eligible, consented, provided with informational session	Recruitment tracking forms; quality checks by PI; weekly meetings with mentor, clinic staff, and research team
Efficacy: Fatigue Emotional distress: anxiety Emotional distress: depressive symptoms Quality of Life Sleep Disturbance Self-Efficacy	PROMIS Fatigue SF 6a(>0.9) ²³ PROMIS Emotional Distress: Anxiety 6a (0.97) ²⁴ PROMIS Emotional Distress: Depressive symptoms SF 6a (0.97) ²⁵ Food Allergy Quality of Life-Parental Burden (>0.85) ²⁶ PROMIS Sleep Disturbance SF 6a (0.9) ²⁷ Food Allergy Self-Efficacy Scale for Parents (0.63-0.89) ²⁸	Tracking forms; fidelity checklist; transmissions from web-based application to PI/RA; post-intervention interviews; weekly meeting with mentor, clinic staff, and research team; baseline, 4-weeks post-intervention, 3-months post-intervention
Measures of self-management behaviors:	# days recorded symptoms; # days and types of recorded treatments/interventions	

Monitoring and tracking symptoms		
Adoption: Adherence	# days symptoms recorded; # times problem-based intervention accessed; length of time in minutes problem-based intervention accessed; # times educational component accessed; length of time in minutes educational component accessed	Tracking forms; data transmitted from web-based application; fidelity checklist; weekly meetings with mentor and research team; caregiver interview at end of study
Acceptability	Caregiver satisfaction; # problems reported; types of problems reported	
Education	# times accessed educational materials; length of time in minutes educational materials accessed	
Symptom monitoring and tracking	# days recorded symptoms	
Implementation: Technology	# problems encountered with mobile device, # problems reported to research staff; types of problems reported	Tracking forms; weekly meeting with mentor and research team; caregiver interview at end of study
Consistency of intervention	instructional session conducted as planned; fidelity to protocol maintained	
Maintenance: Projection of future adoption	# caregivers who would continue intervention; caregiver perception of the intervention	Caregiver interview at end of study; weekly meetings with mentor and team

Sample size considerations

The purpose of this study is to establish feasibility of implementing the integrated intervention and obtain estimates of variability for efficacy outcomes, rather than to confirm or refute hypotheses. The proposed pilot study will recruit N=30 subjects for participation. Because this is a pilot study and thus will not be testing hypotheses or proposing use of inferential statistics, a target sample size of 30 is appropriate.²⁹

D3.7. Data Analysis

Qualitative analyses (Aim 1): Data from observational sessions and key informant interviews with caregivers and providers will be analyzed using conventional content analysis³⁰ and nVivo qualitative data analysis software version 10³¹ to code data into common themes. These themes will be compared to the intervention and the components of the intervention will be adapted based on the thematic findings. A tree diagram may be used to identify the hierarchical structure of themes.

Feasibility processes (Aim 2): For the feasibility trial, we will collect multiple measures informed by the RE-AIM framework to assess feasibility and inform future efficacy and effectiveness trials. Variables will include those pertaining to the study procedures as well as participant variables. Data to be collected are described in Table 1. Specifically, 95% confidence intervals for proportions will be used to estimate dichotomous outcomes including the proportion of caregivers who agree to participate out of the number approached, the proportion adherent to the intervention protocol, i.e. providing daily symptom monitoring/tracking, using the education component, etc. For the continuous feasibility measures (e.g., patient satisfaction scores from patient surveys and end-of-study interview), frequency distributions and the median and mean responses (with 95% confidence intervals) will be obtained.

Outcome measures and estimates of variability (Aim 3): Demographic and clinical variables obtained at baseline will be described via measures of central tendency (mean, median), variability and frequency distributions as appropriate. Additionally, demographic and clinical characteristics for those who adhered to the study protocol (study completers) versus those who did not adhere (non-adherers and drop-outs) will be compared to better describe the population for this study. For continuous measures for the caregiver (fatigue, anxiety, depression, quality of life, sleep disturbance, pain and self-efficacy), the difference between pre and post intervention measurements will be estimated via 95% confidence intervals.

Post-intervention qualitative analyses (Aim 2): Data collected from post-intervention key informant interviews will be analyzed using directed content analysis³⁰ and nVivo qualitative data analysis software version 10.³¹ Consistent with the directed content analysis approach, initial coding categories are identified according to the guiding theoretical model, and for this study, will reflect the RE-AIM domains.

D3.8. Timeline

Activity	Y1Q1	Y1Q2	Y1Q3	Y1Q4	Y2Q1	Y2Q2
Organization, IRB approval						
Adaptation of BBN to FASST						
Interviews with caregivers and providers						
Analysis of interview data						
Tailoring of FASST						
Recruitment						
Intervention delivery (with assessments)						
3-month follow up assessments						
Data analysis, manuscript preparation, grant submission						

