This study aims to test the feasibility of a multi-component, technology-based intervention to promote self-management and symptom management among caregivers of children newly diagnosed with food allergy. To our knowledge, there are no similar interventions specifically designed for this population and purpose. As such, the PI and BS will generate semi-annual qualitative interim analysis reports on a) adverse events; and b) data obtained during phone end-of-study interviews to understand issues related to the uptake, usability, and adoption of this platform among this population. We will evaluate the screening and enrollment procedures, barriers to participation and retention, including, safety, adherence, acceptability, technology problems encountered if any, and user feedback from the participants and providers. This information gained from this structured process will be used to both guide the refinement of the current protocol and to inform the design of a larger efficacy trial. Interim analysis of outcome variables (fatigue, anxiety, and quality of life) was not considered to avoid inexact inferences and increased chance of error due to few data points, as well as potential for bias if interim results were known to the investigators. Therefore, there are no planned stopping rules for this study.

Withdrawal of Subjects

Participants may voluntarily elect to withdraw their consent at any time for any or no given reason while enrolled in the study. The PI may withdraw participants from the study at any time if they decide it is in the participant's best interest, if they do not follow the investigator's instructions, and/or if they fail to maintain to contact with the researchers or attend study visits. Withdrawals of participants may also occur if there is a protocol violation or early study closure. All data gathered from withdrawn participants will be used in the analysis plan under an Intention-to-Treat (ITT) model.

Risks to Subjects

The risks associated with this intervention are not considered greater than those that patients would otherwise be exposed to when receiving normal standard of care (SOC). However, as with all studies, there are inherent risks involved with the conduct of human subject research that gathers Protected Health Information (PHI). Participants will be made aware of these risks during the Informed Consent process. Identified study risks include: Loss of privacy, emotional distress, physical discomfort, and randomization.

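### Does the count of caregivers who would continue the intervention rest on only 5 of the 20 FASST users?

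*Combined protocol and SAP*

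**What the plan says.** The Maintenance row of Table 1 lists the number of "caregivers who would continue intervention; caregiver perception of the intervention", with the sources "Caregiver interview at end of study; weekly meetings with mentor and team". Neither Table 1 nor the text around it says who is interviewed or when the end of study falls.

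Other places bear on the question:

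- Section D3.5 applies RE-AIM to assess, among other domains, "Maintenance of the intervention with 30 caregivers".
- Section D3.5, post-intervention interviews: "Five participants from each study arm will be randomly selected and asked to participate in post-intervention key informant interviews with the PI". They are semi-structured, held in person or by phone, and meant to add depth on access, usability and adherence.
- Section D3.5 also has the PI collect "frequency and patterns of usage data 3 months post-intervention to assess implementation and preliminary evidence of maintenance".
- Section D3.5, Measures: "Participants will complete measures using a mobile tablet device". This applies to all caregivers at baseline, 4 weeks and 3 months post-intervention.
- Aim 2 in the Specific Aims refers to "process measures, surveys, and key informant interviews in 30 caregivers".
- Section F (Interim Analysis) draws on "data obtained during phone end-of-study interviews to understand issues related to the uptake, usability, and adoption of this platform".
- Section D3.7 (Aim 2) names the end-of-study interview, beside patient surveys, as a source of satisfaction scores to be summarised with means, medians and 95% confidence intervals. A separate paragraph sends the post-intervention key informant interviews to directed content analysis.

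**The concern.** Intent to continue is the only count that Table 1 lists under Maintenance, and its only caregiver-level source is an interview with no stated recipients. A reader looking for a description of that interview finds one post-intervention interview with a sample and a procedure, and it takes five caregivers from each arm. If the two are the same, the count comes from a quarter of the FASST arm and half of the control arm, although section D3.5 promises to assess Maintenance in 30 caregivers.

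Two things would then be at stake. The proportion willing to continue would be too imprecise to inform a later trial. Pooling the arms would also over-represent controls, who have Component 1 only. An open-ended interview would be an awkward source for a yes/no count as well, when every caregiver already completes a tablet questionnaire.

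**Working it through.** **Coverage if the key informant interviews were the source.** Arm sizes are 20 FASST and 10 control (Aim 2), and 20 + 10 = 30 reproduces the planned total. With five interviewed per arm, coverage is 5/20 = 25% of FASST users, 5/10 = 50% of controls and 10/30 = 33% overall.

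**Precision under each reading.** Section D3.7 plans 95% confidence intervals for proportions. The exact (Clopper-Pearson) limits for x out of n are

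- lower = 2.5% quantile of Beta(x, n − x + 1)
- upper = 97.5% quantile of Beta(x + 1, n − x), or 1 if x = n

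The documents give no continuation rate, so 80%, 60% and 100% are assumptions.

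| Assumed rate | 5 FASST users asked | 20 FASST users asked |
|---|---|---|
| 80% | 4/5: 28.4% to 99.5% (width 71 points) | 16/20: 56.3% to 94.3% (38 points) |
| 60% | 3/5: 14.7% to 94.7% (80 points) | 12/20: 36.1% to 80.9% (45 points) |
| 100% | 5/5: lower limit 47.8% | 20/20: lower limit 83.2% |

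Wilson intervals at 80% are narrower, with widths of 59 and 34 points, but show the same contrast. If a quarter of the FASST arm were lost (a further assumption, leaving 15), 12/15 gives 51.9% to 95.7% and 9/15 gives 32.3% to 83.7%. The loss of precision is therefore real if only five are asked.

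**Which reading the text supports.**

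1. *Labels in Table 1.* The Efficacy row lists post-intervention interviews, which matches the section D3.5 heading for the five-per-arm interviews. The Adoption, Implementation and Maintenance rows use the other label, the end-of-study caregiver interview. Two labels in one table suggest two activities.
2. *Analysis.* Section D3.7 takes scores with means and intervals from one interview and codes the other for themes.
3. *Scope.* The five-per-arm interviews add depth on access, usability and adherence. Willingness to continue is not among their named topics. Maintenance is set in "Maintenance of the intervention with 30 caregivers".
4. *Usage elsewhere in Table 1.* The baseline caregiver interview, which supplies the demographics, must cover everyone. The same noun at the end of study reads naturally the same way.
5. *Evidence for the subset reading.* Aim 2 mentions only key informant interviews, but the phrase ends in 30 caregivers, not 10. Section F puts phone end-of-study interviews into qualitative reports. Those reports also cover adverse events, so the word qualitative does not identify the key informant interview. Section F also says phone only, where section D3.5 offers a choice.

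Points 1 to 4 favour a separate interview of all caregivers. Point 5 does not outweigh them.

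**The case for a change.** The strongest case for a change is that the protocol leaves the matter to inference. No sentence gives the recipients or timing of the end-of-study interview. The 4-week meeting held with every caregiver names only the Aim 3 measures, and extra payment is described only for key informant interviews. The RE-AIM guidance of the five-per-arm interviews also points to Table 1. Estimation is the purpose of this pilot, so the absence of hypothesis tests does not excuse an undefined denominator. A fixed yes/no item on the tablet would cost almost nothing.

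The first part stands: recipients and timing are unstated. The remedy is less persuasive. An interview of all caregivers can include a yes/no question, so the tablet item offers no clear gain in precision. Placed in the 4-week questionnaire, it could bring forward by about three months a measure that Table 1 ties to the end of the study, since assessments run to 3 months post-intervention. The PI is present while the tablet is completed, so courtesy bias would remain. Satisfaction already draws on surveys in section D3.7, and Maintenance already draws on usage data at 3 months, which are not restricted to a subset.

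**Conclusion.** The concern does not call for a change. The gap is one of description: who receives the end-of-study interview, and when. The better-supported reading is that all caregivers do, and investigators filling the gap sensibly would ask all of them and report the count by arm with its denominator. The widths of 71 and 80 points arise only if the less supported reading is right, and they also rest on assumed continuation rates. Even with all 20 FASST users and an assumed 80%, the interval is 56% to 94%. The plan states no progression threshold for intent to continue, so no stated decision turns on the difference. This conclusion rests on the labels in Table 1 and the split in section D3.7 meaning what they appear to mean. The documents do not confirm that in a single sentence.
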